#### **13.1 GLIA Ocular Surface Disease Symptoms Questionnaire, Clinic & Daily Diary**

The GLIA Ocular Surface Disease Symptoms Questionnaire will be collected in the clinic at every visit (both pre-dose and post-dose at Visit 2) and will be collected via subject daily diary.

A VAS ranging from None to Most Severe will be used to assess subject's symptom severity, by eye, for the following:

- Ocular discomfort
- Dryness
- Grittiness
- Burning
- Stinging
- Foreign body sensation
- Ocular pain
- Conjunctival redness
- Itching
- Mucus discharge
- Photophobia
- Blurred or cloudy vision
- Air flow sensitivity
- Lid redness
- Lid sticking

Subjects will be asked to rate each symptom by placing a vertical mark on the horizontal line to indicate the level of severity. The result (in mm) will be measured from the left endpoint (None) to the slash marked by subject on the line.

For each symptom, a score is derived by converting the measure length to a maximum score of 10 with one decimal place as follows:

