### 13.1.1 ANALYSIS OF GLIA OCULAR SURFACE DISEASE SYMPTOMS QUESTIONNAIRE COLLECTED IN CLINIC

#### The primary analysis (Study Treatment Phase):

For each symptom, an analysis of covariance (ANCOVA) will be used to compare change from baseline between Pro-ocular and placebo with adjustments for baseline symptom score (BASELINE), treatment group (TRT), visit (VISIT), and treatment x visit interaction (TRT\*VISIT) as the explanatory variable. The least squares (LS) means, LS mean differences, SEs, two-sided 95% CIs for the difference in LS means, and two-sided p-values (unadjusted and Benjamini-Hochberg adjusted p-values) will be reported for the treatment effect at each visit and all visits combined. Model effects will also be displayed.

SAS pseudo-code for this model follows:

```
PROC MIXED data=indata order=internal;
  By EYETYPE;
  class TRT VISIT;
  model CFB = TRT BASELINE VISIT TRT*VISIT;
  LSMEANS TRT VISIT TRT*VISIT / CL PDIFF;
run;
```

The ITT population will be used as the primary population using LOCF for imputation.

Sensitivity analyses will include the ITT population and PP population using observed cases.

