### **13.1.2 Analysis of GLIA Ocular Surface Disease Symptoms Questionnaire Collected in Daily Diary**

The individual symptoms collected in the diary will be analyzed including all data across the 70-day treatment period, testing for a treatment effect using a generalized linear model that accounts for repeated measures, with an unstructured correlation structure, including terms for diary day. The LS means, LS mean differences, SEs, two-sided 95% CIs for the difference in LS means, and two-sided p-values will be reported. Model effects will be presented.

SAS pseudo-code for this model follows:

```
PROC MIXED data=indata order=internal;
  class TRT;
  model SYMPTOM = TRT DAY;
  repeated / subject=SUBJ type=UN ;
  random DAY;
  LSMEANS TRT / CL PDIFF;
run;
```

The LS mean (and SE) daily scores will be displayed graphically by treatment group across the 70 days. The mixed effects model analyses will be truncated at Visit 5 and any data presented after Visit 5 will be summarized with continuous descripted statistics.

Individual subject plots will also be presented displaying the subject score by day.

Analyses will be performed on the ITT population using observed cases only.

All Symptom scores collected via diary will be presented in a subject listing.

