### 13.2.1 Analysis of SANDE Questionnaire

The primary and additional analyses for the modify SANDE Questionnaire will be the same as the Glia Ocular Surface Disease Symptoms Questionnaire. Both ANCOVA analyses will be truncated at Visit 5 and any data presented after Visit 5 will be summarized with continuous descripted statistics.

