### 13.5.3 Slit Lamp without Staining

Slit lamp biomicroscopy examinations without staining will be performed at Visit 1 and Visits 3 – 7. The exam will assess the following components, by eye:

- Lids (erythema, edema, lid margin ulceration, lid margin notches, entropion/ ectropion, trichiasis/madarosis, floppy eyelids, hordeolum (stye))
- Conjunctiva (hyperemia, cicatricial changes, pseudomembranes, chalasis)
- Cornea (edema, corneal ulcers, filamentous keratitis, corneal thinning, corneal neovascularization, scars, conjunctival epithelium invasion, limbal thickening)
- Anterior Chamber (cells, flare)
- Lens (status, opacity)

A VAS ranging from None to Most will be used to score each component except for Lens.

The Investigator will mark a vertical slash on the VAS to indicate the level of severity.

The result (in mm), will be measured from left endpoint to the slash marked by the Investigator on the line.

For each component, a score is derived by converting the measure length to a maximum score of 10 with one decimal place as follows:

$$\text{Score} = \text{Measured Result (mm)} * 10 / \text{CRF Scale Length (mm)}$$

The Investigator will classify any abnormal results as Abnormal Clinically Significant (CS), or Abnormal Not Clinically Significant (NCS), including any other pathologies noted by the Investigator.

The Lens status will be classified as Phakic, Pseudophakic or Aphakic. For Phakic lens, the Lens Opacity will be scored as 0, +1, +2, or +3.

All continuous slit-lamp measures will be analysed the same as Glia Ocular Surface Disease Symptoms Questionnaire and the modified SANDE Questionnaire with the following exceptions. Only the ITT populations using observed cases will be performed and no adjustments for multiplicity will be applied.

The abnormal findings will be summarized using counts and percentages for each treatment group at each visit for each eye. Percentages will be based on the number of subjects in each treatment group with responses. Shift tables will also be provided comparing each follow-up visit to baseline.

During the Study Treatment Phase, the changes (or shifts) from baseline will be relative to the Study Treatment Phase baseline. During the Placebo Cross-over Phase, the changes (or shifts) from baseline will be relative to the Placebo Cross-over Phase baseline.

Analyses will be performed on the ITT population using observed data only.

All slit lamp results will be presented in a subject listing.

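### The primary clinic ANCOVA applies one residual variance (and one baseline slope) to every visit, so its each-visit intervals and p-values are calibrated only if residual variance stays the same over the visits

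*SAP*

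**What the plan says.** SAP 13.1.1, primary analysis, gives the model statement "model CFB = TRT BASELINE VISIT TRT*VISIT" and goes straight on to "LSMEANS TRT VISIT TRT*VISIT / CL PDIFF". There is no BASELINE*VISIT term and no REPEATED or RANDOM statement. LS-mean differences, standard errors, 95% intervals, and unadjusted and Benjamini-Hochberg p-values "will be reported for the treatment effect at each visit and all visits combined".

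The model is used again elsewhere. For SANDE (13.2.1) the analyses "will be the same as the Glia Ocular Surface Disease Symptoms Questionnaire". Section 13.5.3 adds that "All continuous slit-lamp measures will be analysed the same as Glia Ocular Surface Disease Symptoms Questionnaire", there without multiplicity adjustment.

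Section 13.1 says the GLIA questionnaire is "collected in the clinic at every visit (both pre-dose and post-dose at Visit 2"). SAP 3.1 gives the post-dose reading its own visit label, and 8.3 places baseline before the first dose. The only cut stated for the ANCOVA is at Visit 5. The VISIT levels in the model are never listed. SAP Table 2 puts the post-dose reading at 30-60 minutes, while the GLIA clinic form in the protocol appendix says 30-90 minutes. SANDE and slit lamp have no Visit 2 reading.

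By contrast, the diary model in 13.1.2 does carry "repeated / subject=SUBJ type=UN".

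**The concern.** The treatment effect may differ by visit in this model, but the yardstick may not. Every per-visit difference gets the same standard error, built from a variance averaged over visits, and is adjusted with a slope averaged over visits. A symptom score marked within about an hour of the baseline score would be expected to follow it closely. A score ten weeks later would be expected to follow it less closely, leaving more residual scatter. If so, averaging lends Day 70 some precision that belongs to the early readings.

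Day 70 is the visit that matches the 70-day objective (SAP 2), and its p-value enters the Benjamini-Hochberg step. A false-positive rate well above 5% there would weaken the result that readers will look at first.

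**Working it through.** **Inputs from the documents.** 33 subjects, 22 + 11, 2:1 (SAP 5); two-sided 0.05 (SAP 8.4); a 0-10 scale (SAP 13.1); one early discontinuation (SAP 16), so complete data are a fair approximation. SAP 5 gives no SD, effect size or power, so there is no planned figure to reproduce beyond 22 + 11 = 33.

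**Inputs assumed.** SD 2.5 unless stated, and the correlations with baseline shown below.

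**Hand calculation, pattern A** (correlation 0.9, 0.7, 0.6, 0.5 at post-dose, Day 14, Day 42, Day 70; constant SD):

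1. Residual variance at a visit = SD² × (1 − r²). With SD² = 6.25 this is 1.19, 3.19, 4.00, 4.69.
2. Slope of change on baseline = r − 1: −0.1, −0.3, −0.4, −0.5. The common slope is their mean, −0.325.
3. Variance added by using the common slope = (own slope − common slope)² × 6.25: 0.32, 0.00, 0.04, 0.19.
4. Pooled variance = mean of (1 + 3) = 3.40. Reported SE = √3.40 × √(1/22 + 1/11) = 1.844 × 0.369 = 0.68 at every visit.
5. True SD of the estimate = √(1 + 3 at that visit) × 0.369: 0.45, 0.66, 0.74, 0.82. Reported over true: 1.50, 1.03, 0.92, 0.83.
6. Residual df = 132 rows − 9 parameters = 123, critical value 1.979. Approximate error at Day 70 = 2 × [1 − Φ(1.979 × 0.835)] ≈ 9.8%. At post-dose = 2 × [1 − Φ(1.979 × 1.504)] ≈ 0.3%.

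**Simulation of the model as written** (20,000 null trials per pattern). Percentage error of the nominal 5% test:

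| Assumed pattern | Post-dose | Day 14 | Day 42 | Day 70 | Day 14/42/70 without post-dose |
|---|---|---|---|---|---|
| A: r 0.9/0.7/0.6/0.5 | 0.4 | 4.7 | 7.5 | 10.6 | 3.4 / 5.7 / 7.7 |
| B: r 0.8/0.7/0.65/0.6 | 2.2 | 4.8 | 6.6 | 8.2 | 4.0 / 5.5 / 6.9 |
| D: r 0.95/0.6/0.5/0.4 | 0.2 | 5.6 | 8.0 | 10.2 | 4.0 / 5.5 / 7.3 |
| E: as A, SD falling 2.5 to 1.8 | 1.8 | 6.0 | 6.5 | 7.0 | 5.5 / 5.8 / 5.3 |
| C: r 0.6 throughout, constant SD | 5.4 | 5.3 | 5.7 | 5.3 | 5.3 / 5.4 / 5.5 |
| F: flat r, SD falling to 1.8 | 8.7 | 6.2 | 4.2 | 2.4 | 7.5 / 5.2 / 3.2 |

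Repeat runs of A and B agreed closely. They gave up to 2.5% at post-dose, and 8.0% at Day 70 for A without the post-dose reading.

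**Which restriction does the damage?**

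- Own slope at each visit, pooled variance kept (A): 0.2/5.0/7.7/10.4%. The error stays.
- Unstructured covariance by subject, common slope kept (3,000 trials each): 5.0/5.2/4.7/5.3% in A, and 4.4-5.3% across B and D. The error goes.
- Own slope and own variance (ANCOVA at each visit, 30 df): 4.7-5.3% at every visit in every pattern.

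So the pooled variance drives the p-value error. The common slope shifts estimates only when baseline is imbalanced: shift = (own slope − common slope) × baseline difference. Among trials where Pro-ocular is more than 1 SE higher at baseline, the mean null difference in A is +0.32 at post-dose and −0.25 at Day 70.

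**Interval width in A.** The model as written gives a mean 95% half-width of 1.34 at all four visits. Per-visit analysis gives 0.83, 1.36, 1.52 and 1.65. At Day 70, 1.65 / 1.34 = 1.23.

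**The case against.** The strongest reply is that nothing in the documents shows the visits to be unlike. Pattern C is near nominal and F reverses the direction. A reader might infer that the per-visit results are certainly wrong, too narrow late and too wide early. The documents do not support that: it needs SDs and correlations they do not give, and even with fading correlation Day 14 error is slightly above 5% in D and E. This objection stands, and the point has to be conditional.

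Second, the post-dose reading is in the model only by inference. That also stands. Inclusion is the natural reading, because the reading has a visit label, follows baseline and is not excluded. The argument from a reading within the hour cannot be carried to SANDE or slit lamp, which have none.

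Third, the fault may be only a symptom of the missing REPEATED statement, which also makes the all-visits-combined test treat one subject's visits as independent (14-19% error in every pattern simulated). This is largely right, and one repair can serve both. But the repair has to be unstructured, since a random intercept or compound symmetry would keep a common variance over visits.

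Fourth, 13.1.1 also plans two-sample t-tests at each visit, which do not pool over visits and held 4.3-5.7% error when simulated. They are a useful cross-check. However, they are additional analyses, not the primary one, and they are not adjusted for baseline.

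A reader might also infer that a real immediate effect would be missed at the post-dose reading. No power calculation supports that, and the stated objective is 70 days of treatment.

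**Conclusion.** The concern holds in conditional form. As coded, the each-visit standard errors, intervals and Benjamini-Hochberg p-values are right only if residual variance is equal at every visit, and the SAP neither states nor justifies that assumption. Under fading correlation with baseline, Day 70 error is about 7-11% with the post-dose reading in the model and about 5-8% without it. Post-dose error is then 0.2-2.5%. These figures assume complete normal data and 22 v 11. The common slope is secondary: under randomisation it does not bias the estimate on average, but it costs some efficiency and shifts estimates after a chance baseline imbalance. The change should be made, because it protects the Day 70 result whichever pattern is true.

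**What to change.** In SAP 13.1.1, and so for SANDE and slit lamp:

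- List the VISIT levels in the model and say whether Visit 2 post-dose is one of them.
- Add REPEATED VISIT / SUBJECT=SUBJ TYPE=UN, with Kenward-Roger degrees of freedom.
- Add BASELINE*VISIT to the MODEL statement, as an efficiency gain and a guard against baseline imbalance.

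This yields valid per-visit contrasts, keeps the all-visits-combined estimate that 13.1.1 requires, and repairs its independence error. A separate ANCOVA at each visit is an equivalent check on the per-visit contrasts with complete data, but alone it would drop the combined estimate.

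No new data are needed. With four visit levels the covariance has 4 × 5 / 2 = 10 parameters instead of 1, plus 3 more slopes; with three levels, 6 and 2. The Day 70 interval widens by about 18% to 23% in the fading-correlation examples (SE 0.332 v 0.281 SD; half-width 1.65 v 1.34), while the post-dose interval narrows. If the visits are in fact alike, little is lost: in C the mean half-width goes from 1.46 to 1.52.

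Separately, reconcile the post-dose timing of 30-60 minutes in the visit schedule with 30-90 minutes on the GLIA clinic form.

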#### Additional analyses:

For each symptom, an analysis of covariance (ANCOVA) will be used to compare change from baseline between Pro-ocular and placebo with adjustments for baseline symptom score (BASELINE), treatment group (TRT), visit (VISIT), eye type (EYETYPE) and treatment x visit interaction (TRT\*VISIT) as the explanatory variable. The least squares (LS) means, LS mean differences, SEs, two-sided 95% CIs for the difference in LS means, and two-sided p-values (unadjusted only) will be reported for the treatment effect at each visit and all visits combined. The model effect will also be displayed.

```
PROC MIXED data=indata order=internal;
  class TRT VISIT;
  model CFB = TRT EYETYPE BASELINE VISIT TRT*VISIT;
  LSMEANS TRT VISIT EYETYPE TRT*VISIT / CL PDIFF;
run;
```

The ITT population using only observed cases will be used for this analysis. Both ANCOVA analyses will be truncated at Visit 5 and any data presented after Visit 5 will be summarized with continuous described statistics. Continuous descriptive statistics will be used to summarize each symptom score by eye type, visit, and treatment group. Change from baseline will also be summarized. Two sample t-tests will be used to compare Pro-ocular to placebo for the visit score and for the change from baseline.

During the Study Treatment Phase, the changes from baseline will be relative to the Study Treatment Phase baseline. During the Placebo Cross-over Phase, the changes from baseline will be relative to the Placebo Cross-over Phase baseline.

Analyses will be performed on the ITT population using observed cases.

All Symptom scores will be presented in a subject listing.

### **13.1.2 Analysis of GLIA Ocular Surface Disease Symptoms Questionnaire Collected in Daily Diary**

The individual symptoms collected in the diary will be analyzed including all data across the 70-day treatment period, testing for a treatment effect using a generalized linear model that accounts for repeated measures, with an unstructured correlation structure, including terms for diary day. The LS means, LS mean differences, SEs, two-sided 95% CIs for the difference in LS means, and two-sided p-values will be reported. Model effects will be presented.

SAS pseudo-code for this model follows:

```
PROC MIXED data=indata order=internal;
  class TRT;
  model SYMPTOM = TRT DAY;
  repeated / subject=SUBJ type=UN ;
  random DAY;
  LSMEANS TRT / CL PDIFF;
run;
```

The LS mean (and SE) daily scores will be displayed graphically by treatment group across the 70 days. The mixed effects model analyses will be truncated at Visit 5 and any data presented after Visit 5 will be summarized with continuous descripted statistics.

Individual subject plots will also be presented displaying the subject score by day.

Analyses will be performed on the ITT population using observed cases only.

All Symptom scores collected via diary will be presented in a subject listing.

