**Efficacy Analyses**

The continuous and ordinal efficacy variables collected at each visit (and time point, where relevant) will be summarized with number of observations (n), mean, standard deviation, median, minimum and maximum. Statistical inference testing will be conducted and the results will be utilized as additional descriptors of the data. Two-sample *t*-tests will be employed for continuous variables. Two-sample *t*-tests, Wilcoxon rank sum tests and analysis of covariance (ANCOVA) models adjusting for baseline will be employed for ordinal variables. For the ANCOVA models, treatment will be compared to the placebo. Pearson's chi-square or Fisher's exact tests (in the case of expected counts less than 5) will be employed for qualitative variables. Where appropriate, the change from baseline for each parameter will also be summarized using descriptive statistics.

The individual symptoms collected in the diary will be analyzed including all data across the 70-day treatment period, testing for a treatment effect using a generalized linear model that accounts for repeated measures with an unstructured correlation structure, including terms for diary day and the treatment-by-day interaction.

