## APPENDICES

## SCHEDULE OF VISITS AND ASSESSMENTS

## Visits 1-7

Blue = Conducted at DFCI		Study Treatment Phase					Placebo Cross-over Phase	
Black = Conducted at MEEI	Visit 1 (Screening)	Visit 2 Baseline & First Drug Application		Visit 3	Visit 4	Visit 5	Visit 6	Visit 7
	Day -14 to -1	Day 1	Day 1	Day 14±2	Day 42±3	Day 70±3	3 weeks	6 weeks
Procedure		Pre-Dose	30-60 min Post-Dose					
2-digit screening number	X							
Informed consent	X							
Visual acuity (current correction)	X					X		
NIH Ocular GvHD Score	X					X		X 
Facial photo		X				X		X
Slit lamp biomicroscopy	X			X	X	X	X	X
Undilated fundoscopy exam	X					X		
Corneal and conjunctival staining	X			X	X	X	X	X
Intraocular pressure	X					X		X
Inclusion/Exclusion criteria	X							
Medical/Ophthalmology history and updates	X	X		X	X	X	X	X
Prior and concomitant medication query	X	X		X	X	X	X	X
Concomitant medications (BMT)	X				X	X		X
Medical history & physical (BMT)	X							
Demographic data	X							
Video of face & eyes (1 minute)		X	X	X	X	X	X	X
TearScan examination		X	X	X	X	X	X	X
Urine pregnancy test	X					X		
Modified SANDE questionnaire	X			X	X	X	X	X
GLIA Ocular Surface Disease Symptoms Questionnaire	X	X	X	X	X	X	X	X
Adverse event query			X	X	X	X	X	X
Screen Pass/Fail	X							
3-digit random number	X							
BMT systemic evaluation & GvHD assessment	X				X	X		X
Standard GvHD, CBC, and metabolic labs	X				X	X		X
Endocrine panel	X				X	X		X
Daily diary and ocular medication log collected				X	X	X	X	X
Study drug collected/ accountability				X	X	X	X	X
Study drug application (in-clinic)		X						
Study drug dispensed		X		X	X	X	X	
Daily diary & ocular medication log dispensed			X	X	X	X	X	

 Added as protocol deviation to original protocol v4.

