**Table 2. Schedule of Visits and Assessments**

Blue = Conducted at DFCI		Study Treatment Phase				Placebo Cross-over Phase	
Black = Conducted at MEEI	Visit 1 (Screening)	Visit 2 Baseline & First Drug Application	Visit 3	Visit 4	Visit 5	Visit 6	Visit 7
	Day -14 to -1	Day 1	Day 1	Day 14±2	Day 42±3	Day 70±3	3 weeks
Procedure		Pre-Dose	30-60 min Post-Dose				
2-digit screening number	X						
Informed consent	X						
Visual acuity (current correction)	X					X	
NIH Eye Score	X					X	X
Facial photo		X				X	X
Slit Lamp Biomicroscopy	X			X	X	X	X
Undilated Fundoscopy Exam	X					X	
Corneal and Conjunctival Staining	X			X	X	X	X
Intraocular Pressure	X					X	X
Inclusion/Exclusion Criteria	X						
Medical/Ophthalmology history and updates	X	X		X	X	X	X
Prior and concomitant medication query	X	X		X	X	X	X
Concomitant medications (BMT)	X				X	X	X
Medical History & Physical (BMT)	X						
Demographic data	X						
Video of face & eyes (1 minute)		X	X	X	X	X	X
TearScan Examination		X	X	X	X	X	X
Urine pregnancy test	X					X	
Modified SANDE Questionnaire	X			X	X	X	X
GLIA Ocular Surface Disease Symptoms Questionnaire	X	X	X	X	X	X	X
Adverse Event Query			X	X	X	X	X

Blue = Conducted at DFCI		Study Treatment Phase					Placebo Cross-over Phase	
Black = Conducted at MEEI	Visit 1 (Screening)	Visit 2 Baseline & First Drug Application		Visit 3	Visit 4	Visit 5	Visit 6	Visit 7
	Day -14 to -1	Day 1	Day 1	Day 14±2	Day 42±3	Day 70±3	3 weeks	6 weeks
Screen Pass/Fail	X							
3-digit random number	X							
BMT systemic evaluation & GvHD assessment	X				X	X		X
Standard GvHD, CBC, and metabolic labs	X				X	X		X
Endocrine panel	X				X	X		X
Daily diary collected				X	X	X	X	X
Study drug collected/ accountability				X	X	X	X	X
Study drug application (in-clinic)		X						
Study Drug Dispensed		X		X	X	X	X	
Daily Diary Dispensed			X	X	X	X	X	

Abbreviations: CBC = Complete Blood Count, DFCI = Dana-Farber Cancer Institute, GvHD = graft-versus-host disease, MEEI = Massachusetts Eye and Ear Infirmary.

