## **8.3 Definition of Baseline**

For the Study Treatment Phase, baseline is defined as the last measurement prior to the first dose of study medication.

For the Cross-over Phase, baseline is defined as the last measurement prior to the first dose of Pro-ocular™ 1% topical gel, which is expected to start on the day after Visit 5.

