Listing 16.2.8.5	Laboratory Results - Endocrine Panel	All Subjects
Figures	Title	Population
Figure 14.2.1.1	GLIA Ocular Surface Disease Symptoms Questionnaire, in Clinic in the Worse Eye by Symptom	ITT Population
Figure 14.2.1.2	GLIA Ocular Surface Disease Symptoms Questionnaire, Daily Diary in the Worse Eye by Symptom	ITT Population
Figure 14.2.2.1	Modified SANDE - Symptom Assessment iN Dry Eye (SANDE) Questionnaire in the Worse Eye by Symptom	ITT Population

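### The diary model omits a baseline covariate that the trial already collects, which costs precision and leaves an additional endpoint exposed to chance imbalance

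*SAP*

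**What the plan says.** The diary analysis in SAP 13.1.2 is a repeated-measures model "with an unstructured correlation structure, including terms for diary day". Its code reads "model SYMPTOM = TRT DAY", with the raw score as outcome. Neither the prose nor the code names a baseline or an eye-type term. The protocol's version (Efficacy Analyses), "including terms for diary day and the treatment-by-day interaction", has no baseline term either.

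The clinic analysis of the same questionnaire (SAP 13.1.1) is run by eye type with "model CFB = TRT BASELINE VISIT TRT*VISIT".

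SAP 13.1 has the questionnaire completed in clinic at every visit, including before dosing at Visit 2, and again in the daily diary. Both use the same 15 items, scored for each eye.

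In the SAP schedule (Table 2) the row "Daily Diary Dispensed" has its first mark in the post-dose column of Visit 2. The protocol row "Daily diary & ocular medication log dispensed" (appendix schedule, Visits 1-7) shows the same. The in-clinic application is marked in the pre-dose column.

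Under SAP 8.3, "baseline is defined as the last measurement prior to the first dose of study medication". SAP 8.1 and 13 make the worse eye at baseline, determined symptom by symptom, the unit of efficacy analysis. SAP 19 lists diary tables by eye and for combined eyes, and a figure titled "GLIA Ocular Surface Disease Symptoms Questionnaire, Daily Diary in the Worse Eye by Symptom".

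**The concern.** By the two schedules, no diary page can precede the first dose, so the diary has no baseline of its own under SAP 8.3. That need not matter, because the same items are scored in clinic on Day 1 before dosing. The diary model does not use that score.

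With 33 subjects split 22 to 11, arms can differ noticeably at baseline by chance. Part of any such difference carries into the diary treatment effect, and between-subject variation that the baseline could explain stays in the error. SAP 13.1.2 reports confidence intervals and two-sided p-values for each diary symptom. Clinic and diary results on one questionnaire could therefore disagree partly because only one of them is adjusted.

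A smaller gap is that SAP 13.1.2 does not name the measurement that fixes the worse and fellow eye for the diary outputs. The diary form adds to the uncertainty, because its score columns are headed Baseline although the form is handed out after the first application.

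**Working it through.** **Inputs.** Allocation of 22 and 11 comes from SAP 5. Two-sided alpha of 0.05 comes from SAP 8.4. The documents give no SD, effect size, power or baseline-to-diary correlation, so there is no planned figure to reproduce. Results are in SD units, and the correlation r between the Visit 2 pre-dose clinic score and a subject's mean diary score is assumed at 0.3, 0.5 and 0.7. The low value is included because one clinic reading is being set against 70 days of home ratings.

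**Chance imbalance.**
- SE of a difference in means = sqrt(1/22 + 1/11) = 0.369 SD.
- Expected absolute imbalance = 0.369 × sqrt(2/π) = 0.29 SD per symptom.
- P(|imbalance| > 0.5 SD) = P(|Z| > 0.5/0.369) = 17.6% per symptom.

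**What a 0.5 SD imbalance does to the unadjusted effect.** The shift is r × 0.5. The conditional type I error is the chance that the unadjusted test rejects, given that imbalance and no treatment effect. The critical value is 1.96 × 0.369, and the estimate has mean r × 0.5 and SE 0.369 × sqrt(1 − r²).

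| Assumed r | Shift (SD) | Conditional type I error |
|---|---|---|
| 0.3 | 0.15 | 5.8% |
| 0.5 | 0.25 | 7.0% |
| 0.7 | 0.35 | 7.8% |

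These figures are conditional on the imbalance. Averaged over randomisation, the unadjusted comparison is unbiased.

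**What adjustment buys.** In a simple two-mean approximation, residual variance is multiplied by 1 − r², so the equivalent unadjusted sample is 33/(1 − r²). The detectable difference at 80% power is (1.960 + 0.842) × 0.369 × sqrt(1 − r²). The last column takes a true effect of 0.8 SD, which is also an assumption.

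| Assumed r | 1 − r² | Equivalent N | Gain in subjects | Detectable difference (SD) | Power at 0.8 SD |
|---|---|---|---|---|---|
| No baseline | 1.00 | 33 | none | 1.03 | 58% |
| 0.3 | 0.91 | 36 | 10% | 0.99 | 62% |
| 0.5 | 0.75 | 44 | 33% | 0.90 | 71% |
| 0.7 | 0.51 | 65 | 96% | 0.74 | 86% |

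Exact t-based power is slightly lower: 56% without baseline, then 59%, 68% and 84%.

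**Worse eye.** SAP 13 determines the worse eye for each symptom, not for each instrument. SAP 8.1 ties it to baseline, and SAP 8.3 makes baseline the last pre-dose measurement. Read together, they point to the Visit 2 pre-dose clinic score, with Visit 1 as the natural fallback. SAP 13.1.2 does not say so for the diary.

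**The case against.** **Importance.** SAP 2.2 lists the diary as an additional efficacy variable, outside the key set that receives the multiplicity adjustment in SAP 8.5. The protocol treats inferential tests as further description of the data, and its own diary model has no baseline term. The key clinic analysis already adjusts. All of this stands and limits the point's weight.

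**Validity.** A reader might infer that the omission biases the diary result, or that a baseline imbalance passes in full into the treatment effect. Neither follows. Treatment is randomised, the unadjusted standard error already includes this variation, and an imbalance carries over only in proportion to r.

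**Post-dose selection of the eye.** A reader might also infer that the worse eye would be picked from the first diary page, after the gel may have begun to act. The protocol's background section does report early relief in earlier use. But no section says the eye would be picked that way, and doing so would contradict SAP 8.3. The Baseline heading on the diary form is a reason to clarify, not evidence of such a plan.

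**Size of the gain.** The gains come from a two-mean approximation, not from the planned model. An unstructured matrix over 70 days has 70 × 71/2 = 2,485 parameters for 33 subjects, and a baseline term does nothing about that. The gains are therefore indicative only.

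**Timing of the diary.** The statement that no diary entry precedes dosing rests on the two schedules, because the Visit 2 procedure list was not in the text available. The schedules agree with each other.

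**Conclusion.** The point holds as one of precision. The diary model leaves out a same-instrument, same-symptom, same-eye score taken before dosing, while the clinic analysis of that questionnaire uses its baseline. The cause is the model's omission, not the lack of a pre-dose diary page.

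Each symptom has a 17.6% chance of a baseline imbalance above 0.5 SD. The gain from adjusting runs from about 10% more subjects at r = 0.3 to 96% at r = 0.7. The upper end should not be quoted alone, since the correlation is assumed throughout.

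No systematic bias is shown, and the affected endpoint is additional rather than key. On the worse eye, the general rules already give a pre-treatment answer, so only a clarifying statement is missing.

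**What to change.** In SAP 13.1.2, add a sentence to this effect: for all diary analyses and outputs, baseline is the Visit 2 pre-dose clinic GLIA score for the same symptom and eye (Visit 1 if missing), and that score defines the worse and fellow eye. Then add the term, for example `model SYMPTOM = BASELINE TRT DAY` with any other day terms retained, and fit it separately by eye type as SAP 13 already intends. The sentence should also make clear that the Baseline heading on the diary form does not denote a pre-dose measurement.

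The cost is one SAP sentence, one model term and one degree of freedom. No new data are needed. The change belongs in the SAP before the primary database lock.
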